## RECORDS ON REVISIONS

Version	Date	Author	Remarks
Version 1.0	27 June, 2017	[REDACTED]	First version Collaborators: [REDACTED]
Version 1.1	3 July, 2017	[REDACTED]	Formatting changes were made.
Version 2.0	6 July, 2017	[REDACTED]	9.2 15) Analysis population was changed and writing error was corrected.

---

## 1. INTRODUCTION

This document describes the statistical methods to be used in the summary and analysis of data from Protocol 1601T0831. All decisions regarding final analysis, as defined in this statistical analysis plan (SAP), have been made prior to unblinding/database lock of the study data. Table, listing and figure mock-ups are described in the TLF shell document prepared separately. Details of the analyses of pharmacokinetics and pharmacokinetics/pharmacodynamics will also be described in a separate document.

All the analyses described in the SAP will be performed in the Biostatistics Dept., Shionogi & Co., Ltd.

## 2. OVERVIEW

This is a randomized, double-blind, multicenter, parallel-group, placebo- and active controlled study enrolling approximately 1494 patients diagnosed with influenza. Approximately 1350 patients aged 20 to 64 years and 144 patients aged 12 to 19 years will be enrolled. Patients in 20 to 64 years age stratum will be randomly assigned in a ratio of 2:2:1 to receive a single dose of 40 or 80 mg of S-033188 according to their weight category, 75 mg BID of oseltamivir for 5 days, or placebo. With the aim to achieve a broadly comparable exposure, patients who weigh < 80 kg at Screening will receive 40 mg of S-033188, and patients who weigh  $\geq$  80 kg at Screening will receive 80 mg of S-033188. Patients in 12 to 19 years age stratum will be randomly assigned in a ratio of 2:1 to receive a single dose of 40 or 80 mg (depending on weight) S-033188 or placebo.

For the schedule of this study, see Appendix 1.

## 3. SUTDY OBJECTIVES

### 3.1 Primary Objective

- To evaluate the efficacy of a single, oral dose of S-033188 compared with placebo by measuring the time to alleviation of symptoms in patients with uncomplicated influenza virus infection.

### 3.2 Secondary Objective

- To evaluate the efficacy of a single, oral dose of S-033188 compared with oseltamivir 75 mg twice daily (BID) for 5 days by measuring the time to alleviation of symptoms in patients aged 20 to 64 years with uncomplicated influenza virus infection
- To evaluate the efficacy of a single, oral dose of S-033188 compared with placebo by measuring the secondary endpoints in patients with uncomplicated influenza virus infection
- To evaluate the efficacy of a single, oral dose of S-033188 compared with oseltamivir 75 mg BID for 5 days by measuring the secondary endpoints in patients with uncomplicated influenza virus infection

### **3.3 Other Efficacy Objective**

- To evaluate the polymorphic and treatment-emergent amino acid substitutions in the polymerase acidic protein (PA) gene and drug susceptibility in patients with evaluable virus

### **3.4 Safety Objectives**

- To compare the safety and tolerability of a single dose of S-033188 with placebo
- To compare the safety and tolerability of a single dose of S-033188 with oseltamivir 75 mg BID for 5 days
- To compare the frequency of adverse events (AEs) in patients with influenza of a single dose of S-033188 with oseltamivir 75 mg BID for 5 days and with placebo

### **3.5 Pharmacokinetic Objectives**

- To determine the pharmacokinetics (PK) of the active form of S-033188, ie, S-033447, in patients with uncomplicated influenza virus infection

### **3.6 Health Economic Outcomes Research Objective**

- To compare the total quality-of-life change by measuring the EuroQol-5 Dimensions-5 Levels (EQ-5D-5L) and a work productivity (WP) questionnaire in patients treated with S-033188 compared with oseltamivir 75 mg BID for 5 days and placebo

## **4. OUTLINE OF STUDY DESIGN**

### **4.1 Study Blinding**

The study will be conducted in a double-blind, double-dummy fashion by using placebo matching S-033188 and oseltamivir in appearance, labeling, and packaging.

### **4.2 Allocation Procedure**

Patients in 20 to 64 years age stratum will be randomized on a 2:2:1 basis to S-033188 group, oseltamivir group, or placebo group. Patients in 12 to 19 years age stratum will be randomized on a 2:1 basis to either S-033188 group or placebo group. An interactive response technology (IRT) will be used to assign patients to numbers for which treatment has already been randomly assigned. The randomization will also be stratified by region

(Japan/Asia, Rest of the world), body weight (< 80 kg, ≥ 80 kg) and baseline composite symptom score (≤ 11, ≥ 12).

### **4.3 Target Sample Size**

The required sample size of the intention to treat infected (ITTI) Population will be 968 (93 patients in 12 to 19 years age stratum and 875 patients in 20 to 64 years age stratum).

It is assumed that the RT-PCR positive rate for influenza A or B virus will be 65%. Therefore, 1494 patients (144 patients in 12 to 19 years age stratum and 1350 patients in 20 to 64 years age stratum) will be randomized to ensure an adequate number of patents in the ITTI Population.

The primary analysis will be to compare time to alleviation of symptoms between the S-033188 group and the placebo group (both age strata combined). Based on the results of S-033188 Phase 2 study and the three placebo-controlled studies of oseltamivir, the difference between S-033188 and placebo will be assumed to be 28 hours. If the ratio of the median time to alleviation between the S-033188 group and the placebo group remains the same (i.e. 0.64: 49.5/77.7) in the proposed study, the difference can further be assumed to be 36 hours (64 hours in the S-033188 group, 100 hours in the placebo group). Patients will be randomized on a 2:1 basis to either S-033188 or placebo and the follow-up period will be 336 hours (14 days). Assuming that time to alleviation follows an exponential distribution, the study requires 618 patients in the ITTI Population in order for the stratified generalized Wilcoxon test to have 90% or more power with a two-sided significance level of 0.05. Assuming that the percentage of the number of patients in 12 to 19 years age stratum is 15%, the required breakdown will be 93 patients in 12 to 19 years age stratum (62 patients for the S-033188 group and 31 patients for the placebo group), 525 patients in 20 to 64 years age stratum (350 patients for the S-033188 group and 175 patients for the placebo group).

Using a 1:1 randomization ratio between the S-033188 and oseltamivir, ITTI Population of oseltamivir will be 350 patients to compare time to alleviation of symptoms between the S-033188 and the oseltamivir in 20 to 64 years age stratum. Table 1 shows the statistical power to compare between the S-033188 group and the oseltamivir group under several sets of difference in time to alleviation of symptoms.

**Table 1                      Statistical Power to Compare between S-033188 and Oseltamivir**

Median time to alleviation of symptoms (S-033188 group, oseltamivir group)	Statistical power for comparison between the S-033188 group and the oseltamivir group by stratified generalized Wilcoxon test
(72 hours, 84 hours)	42.1%
(70 hours, 84 hours)	54.8%
(68 hours, 84 hours)	67.4%
(66 hours, 84 hours)	78.5%
(64 hours, 84 hours)	87.2%

## 5. ANALYSIS POPULATIONS

### 5.1 Efficacy Populations

The definitions of the Intention-To-Treat-Infected (ITTI) Population and the Per-Protocol Set (PPS) as efficacy populations are provided below. In this study, the ITTI Population is the primary analysis population. The PPS is the secondary analysis population, and data from the PPS will be used to perform a sensitivity analysis for the primary analysis.

The following analysis populations will be analyzed for this study based on enrolled patients with GCP compliance:

1) ITTI Population

This population includes all patients who receive the study drug with a confirmed diagnosis of influenza virus infection. Confirmation of influenza virus infection will be based on the results of RT-PCR on Day 1. The population will be analyzed according to the treatment to which the patients were randomized.

2) Per-Protocol Set (PPS)

This population includes all subjects included in the ITTI Population and did not meet any of the following conditions:

- Ineligible subjects
- Subjects with non-compliance of treatment
  - Treatment compliance rate is less than 60%. The definition of treatment compliance rate shown in 8.1 will be used.
- Subjects with inadequate follow-up
  - Subjects have no symptom data after initial treatment
- Subjects with prohibited medication
- Subjects with incorrect treatment allocation

3) Safety population

This population includes all randomized patients who receive at least one dose of the study drug. The population will be analyzed according to the initial treatment that the patients actually received.

## 6. HANDLING OF DATA IN ANALYSES

### 6.1 Statistical Analysis

Unless otherwise noted, continuous variables will be summarized by using the number of non-missing observations, arithmetic mean, standard deviation (SD), median, minimum, and maximum values as summary statistics; categorical variables will be summarized by using the frequency count and the percentage of subjects in each category as summary statistics.

Subject study data, including data not appearing in tables, will be presented in by-subject data listings. In general, all tables will be presented by treatment group. Individual

subject data and any derived data will be presented by treatment and subject. All analyses and tabulations will be performed by using the SAS Version 9.2 or higher.

## 6.2 Statistical Tests

All statistical tests will be performed at the 0.05 significance level using two-sided tests, unless otherwise noted.

The primary endpoint will first be compared between the S-033188 and placebo groups (primary analysis). Together with the primary efficacy analysis, comparison between the S-033188 and the oseltamivir groups (secondary analysis) will be conducted. For the submission to countries other than Japan, only if statistically significant difference will be observed in primary analysis, secondary analysis will be performed in order to maintain control of overall Type I error.

## 6.3 Acceptable Time Windows for Investigations, Observations, and Examinations

The acceptable time windows shown in Table 2-1 and 2-2. The acceptable time windows shown in Table 2-1 will be used to collect data from the patient diary.

**Table 2-1 Acceptable Time Windows for Parameters of the Patient Diary**

Time Point	Specified Assessment Time Point	Acceptable Time Window
12 hours post-dose	Time of first dosing + 12 hours	Between $\geq 6$ and $< 18$ hours after first dosing
24 hours post-dose	Time of first dosing + 24 hours	Between $\geq 18$ and $< 30$ hours after first dosing
36 hours post-dose	Time of first dosing + 36 hours	Between $\geq 30$ and $< 42$ hours after first dosing
48 hours post-dose	Time of first dosing + 48 hours	Between $\geq 42$ and $< 54$ hours after first dosing
60 hours post-dose	Time of first dosing + 60 hours	Between $\geq 54$ and $< 66$ hours after first dosing
72 hours post-dose	Time of first dosing + 72 hours	Between $\geq 66$ and $< 78$ hours after first dosing
84 hours post-dose	Time of first dosing + 84 hours	Between $\geq 78$ and $< 90$ hours after first dosing
96 hours post-dose	Time of first dosing + 96 hours	Between $\geq 90$ and $< 102$ hours after first dosing
108 hours post-dose	Time of first dosing + 108 hours	Between $\geq 102$ and $< 114$ hours after first dosing
120 hours post-dose	Time of first dosing + 120 hours	Between $\geq 114$ and $< 126$ hours after first dosing
132 hours post-dose	Time of first dosing + 132 hours	Between $\geq 126$ and $< 138$ hours after first dosing
144 hours post-dose	Time of first dosing + 144 hours	Between $\geq 138$ and $< 150$ hours after first dosing
156 hours post-dose	Time of first dosing + 156 hours	Between $\geq 150$ and $< 162$ hours after first dosing
168 hours post-dose	Time of first dosing + 168 hours	Between $\geq 162$ and $< 174$ hours after first dosing
180 hours post-dose	Time of first dosing + 180 hours	Between $\geq 174$ and $< 186$ hours after first dosing
192 hours post-dose	Time of first dosing + 192 hours	Between $\geq 186$ and $< 198$ hours after first dosing
204 hours post-dose	Time of first dosing + 204 hours	Between $\geq 198$ and $< 210$ hours after first dosing
216 hours post-dose	Time of first dosing + 216 hours	Between $\geq 210$ and $< 222$ hours after first dosing
240 hours postdose	Time of dosing + 240 hours	Between $\geq 228$ and $< 252$ hours after dosing
264 hours postdose	Time of dosing + 264 hours	Between $\geq 252$ and $< 276$ hours after dosing
288 hours postdose	Time of dosing + 288 hours	Between $\geq 276$ and $< 300$ hours after dosing

Time Point	Specified Assessment Time Point	Acceptable Time Window
312 hours postdose	Time of dosing + 312 hours	Between $\geq 300$ and $< 324$ hours after dosing
336 hours postdose	Time of dosing + 336 hours	Between $\geq 324$ and $< 348$ hours after dosing
528 hours postdose	Time of dosing + 528 hours	Between $\geq 456$ and $< 600$ hours after dosing

The acceptable time windows shown in Table 2-2 will be used for the assessment of items other than data from the patient diary.

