7.4.1.2 Assessment of Severity of Influenza Symptoms

The patient will self-assess 7 symptoms associated with influenza (cough, sore throat, headache, nasal congestion, feverishness or chills, muscle or joint pain, and fatigue) on a 4-point rating scale (0, None; 1, Mild; 2, Moderate; 3, Severe).

The patient will assess, and record on a paper questionnaire, influenza symptoms predose on Day 1; then subsequent influenza symptoms will be assessed and recorded in the patient eDiary twice daily (morning and evening) until Day 9 and once daily (evening) from Days 10 to 14. Table 7-2 provides the time windows of assessment as a guide.

Table 7-2 Time Windows of Assessment as a Guide: Assessment of Severity of Influenza Symptoms

Assessment period	Time period of a day	Time window as a guide
Day 1 - Day 9	Morning	- 11:59
	Evening	18:00 -
Day 10 - Day 14	Evening	18:00 -

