**Table 2-2 Acceptable Time Windows for Parameters Other than Data from the Patient Diary**

Time Point	Acceptable Time Window
Pre-dose at Visit 1 (Day 1: Day -2 to Day1)	Predose from Day -2 to Day 1 for safety assessment
Pre-dose at Visit 1 (Day 1)	Predose on Day 1 for efficacy assessment
Post-dose at Visit 1 (Day 1)	QOL assessment with EQ-5D-5L questionnaire: by 0.5 hour post-dose on Day 1 Other measurements: 0.5 to 4 hours post-dose on Day 1
Visit 2 (Day 2)	Day 2
Visit 3 (Day 3)	Between Day 3 and Day 4
Optional-Visit 1 (Day 4)	Day 4
Visit 4 (Day 5)	Between Day 5 and Day 6
Optional Visit 2 (Day 6)	Day 6
Visit 5 (Day 9)	Between Day 7 and Day 11
Visit 6 (Day 15)	Between Day 12 and Day 18
Visit 7 (Day 22)	Between Day 19 and Day 25
Early termination	Date of early termination + 3 days

Measurements collected within the acceptable time window for each scheduled assessment time point, including data obtained at the time of withdrawal, will be used for the analyses of all endpoints at each assessment time point. For all patients with multiple measurements within a visit window, the measurement obtained closest to the target time point will be used. If two measurements collected with the same time deviation exist before and after the target time point, the measurement obtained before the target time point will be adopted for analysis. The assessment time point having no measurements within the corresponding acceptable time window will be considered as missing.

In the patient diary, if there are multiple measurements which may be adopted for a scheduled assessment, even though the above rules have been strictly followed, the measurements of the earlier assessment date or the earlier assessment time of day will be adopted (with the priority given to morning, followed by afternoon, evening, and bedtime, in this order). If multiple measurements collected with the same time (date and hour) for body temperature, the highest measurement will be adopted.

In the assessment of items from other than the patient diary, if there are multiple measurements which may be adopted for a scheduled assessment time point (even though the above rules have been strictly followed), the measurements at the time point entered in the CRF will be adopted.

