## **6.5 Definition**

### **6.5.1 Display of Days of Study**

The date of the first dose and the day before the first dose of the S-033188/Placebo will be designated as Day 1 and Day -1, respectively.

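### SAP Table 2-1 assigns no time point to diary entries from 222 to 228 hours, which removes the 216-hour symptom value for patients dosed by noon; its last row is also 24 hours late for Day 22

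*SAP*

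**What the plan says.** SAP 6.3 applies Table 2-1 to patient diary data. Rows from 12 to 216 hours are the target ±6 hours and abut one another. The last of them, 216 hours, is "Between $\geq 210$ and $< 222$ hours after first dosing". From 240 hours the rows are the target ±12 hours, starting with "Between $\geq 228$ and $< 252$ hours after dosing". The final row, 528 hours, is "Between $\geq 456$ and $< 600$ hours after dosing". SAP 6.3 adds: "The assessment time point having no measurements within the corresponding acceptable time window will be considered as missing".

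Protocol 7.4.1.2 has symptoms recorded "twice daily (morning and evening) until Day 9 and once daily (evening) from Days 10 to 14", and its Table 7-2 puts the evening entry at 18:00 or later as a guide. SAP 6.5.1 makes the date of first dosing Day 1.

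SAP 9.2 lists 216 hours as a time point for the proportion of patients with symptoms alleviated (item 9) and for the change from baseline in composite symptom score (item 13). SAP 9.4 tests both at each scheduled time point, by Mantel-Haenszel and ANCOVA respectively. SAP section 9 makes each comparison against placebo and against oseltamivir.

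For Visit 7 (Day 22), SAP Table 2-2 accepts data "Between Day 19 and Day 25", as does Protocol Table 7-6.

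**The concern.** The ±6-hour rows and the ±12-hour rows were not joined, and the six hours left out are where many Day 10 evening entries fall. Day 10 has no scheduled morning symptom entry to take their place. Valid, on-schedule entries would be discarded, and the patients who keep a 216-hour value would be selected by the time of day they were dosed. The 216-hour results would then describe mainly afternoon-dosed patients and would not be comparable with those at 192 hours.

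The last row raises a separate question. Day 22 is the only diary assessment scheduled after Day 14 (the EQ-5D-5L, Protocol 7.7.4.1 and SAP 9.3 item 4), and 528 hours is not Day 22 when the dosing date is Day 1.

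**Working it through.** **Inputs.** Window limits come from SAP Table 2-1, the diary schedule from Protocol 7.4.1.2 and day numbering from SAP 6.5.1. Let h be the clock time of first dosing, e the clock time of the evening entry, and x = e − h in hours. The documents give no distribution for h or e, so the percentages below are assumptions shown over a range.

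**The table's own pattern.** The stated limits reproduce as 216 ± 6 = 210 to 222, 240 ± 12 = 228 to 252, and 528 ± 72 = 456 to 600. Between 6 and 348 hours the only break is 222 to 228.

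**Where the entries fall.** The evening entry on Day d is at (d − 1) × 24 + x hours.
- Day 9 evening: 192 + x. It reaches 210 only if x ≥ 18, which is unrealistic for dosing at a study center.
- Day 10 morning: no symptom entry is scheduled.
- Day 10 evening: 216 + x. It is below 222 only if x < 6.
- Day 11 evening: 240 + x, already past the 216-hour window.

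A 216-hour value therefore requires x < 6. For 6 ≤ x < 12 the Day 10 entry falls in no row; for x ≥ 12 it falls in the 240-hour row. Dosing at or before 12:00 with an entry at or after 18:00 gives x ≥ 6, hence no 216-hour value.

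Example: dosed at 10:00, entries at 20:00, x = 10. Day 9 is at 202 hours (204-hour row), Day 10 at 226 hours (no row), and Day 11 at 250 hours (240-hour row).

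**Size, with uniform h and e.** The condition is h later than e − 6.
- Dosing 09:00-18:00, entries 18:00-22:00: e − 6 averages 14:00, so the share is (18 − 14)/9 = 44%.
- Entries to 20:00: (18 − 13)/9 = 56%. Entries to 24:00: (18 − 15)/9 = 33%.
- Dosing extended to 20:00: (20 − 14)/11 = 55% with entries to 22:00, and (20 − 13)/11 = 64% with entries to 20:00.

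| Dosing | Evening entry | Has 216 h value now | With window to 228 h |
|---|---|---|---|
| 09:00-18:00 | 18:00-20:00 | 56% | 100% |
| 09:00-18:00 | 18:00-22:00 | 44% | 99% |
| 09:00-18:00 | 18:00-24:00 | 33% | 92% |
| 09:00-13:00 | 18:00-22:00 | 3% | 97% |
| 13:00-18:00 | 18:00-22:00 | about 77% | 100% |
| 08:00-12:00 | 18:00-22:00 | 0% | 88% |
| 08:00-12:00 | 18:00-24:00 | 0% | 67% |
| 07:00-12:00 | 18:00-24:00 | 0% | 58% |

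For comparison, the 192-hour row can also use the Day 9 morning entry. With dosing 09:00-18:00 and evening entries 18:00-22:00, a morning entry assumed uniform over 07:00-11:00 gives about 97% with a 192-hour value (87% for 06:00-08:00, 99% for 08:00-12:00).

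With 44% observed, the standard error at 216 hours is about 1/√0.44 = 1.5 times that with full data.

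**Last row.** Day 22 at the dosing clock time is (22 − 1) × 24 = 504 hours. The label 528 is 22 × 24, which is Day 23 (528/24 + 1). The limits 456 and 600 hours are Day 20 and Day 26 at the dosing clock time. A Day 19 visit is at 18 × 24 = 432 hours plus a clock difference of less than 24 hours, so it is always below 456. A Day 20 visit earlier in the day than the dose is also lost.

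**The case against.** The arithmetic is not in dispute; its cause, size and importance are.

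- **Cause.** An entry at 222 to 228 hours is 6 to 12 hours late for a 216-hour target. The ±6-hour tolerance would exclude it even if the 240-hour row began at 222. The underlying cause is that 216 hours is Day 10 at the dosing clock time and Day 10 has no morning symptom entry. This stands. It means the gap must be closed by extending the 216-hour row, and that patients with x ≥ 12 are not recovered.
- **Size.** No document gives dosing or entry times, so 44% is one scenario; 33% to 64% is the fairer statement for all-day dosing. Recovery among morning-dosed patients can be as low as 58%. This also stands, but the direction is the same throughout.
- **Importance.** One of 11 time points is affected, for two secondary endpoints outside the Type I error hierarchy. By 216 hours most patients should have alleviated: under the protocol's exponential medians of 100 and 72 hours, 1 − 2^(−216/100) = 78% and 1 − 2^(−216/72) = 88%. Dosing time precedes any treatment effect and the trial is blinded, so no bias between arms follows. All of this is accepted.
- **Day 22.** A visit on Day 22 itself still falls inside 456 to 600 hours. SAP 9.3 defines the EQ-5D-5L by study day and mentions records labelled as visit records, so Table 2-2 might be meant to govern. That ambiguity is real. However, SAP 6.3 sends diary data to Table 2-1, and Protocol 7.4.1.4 records the EQ-5D-5L in the diary, so Table 2-1 is the plain reading. The EQ-5D-5L is summarized without a test.

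**Conclusion.** The concern holds. The gap from 222 to 228 hours is on the page and needs no assumption. Nor does its main consequence: a patient dosed by noon who follows the guide times has no 216-hour symptom value. How many patients that affects depends on dosing and entry times the documents do not give: 44% with a value in the central scenario and 33% to 64% over the other all-day ranges.

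The harm is lost precision and a 216-hour sample selected by time of dosing, in two tested secondary endpoints. Body temperature keeps a Day 10 morning entry (Protocol 7.4.1.1). The primary endpoint is defined on actual assessment times and is unaffected.

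The 528-hour row is 24 hours late under the SAP's day numbering. If Table 2-1 governs the Day 22 EQ-5D-5L, as SAP 6.3 reads, every permitted Day 19 record is dropped. The plan should be corrected on both points, but neither threatens its main conclusion.

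**What to change.** Change two rows of SAP Table 2-1.

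1. **216 hours:** accept ≥ 210 to < 228 hours, so that the row abuts the 240-hour row. For x < 12 the 240-hour row keeps its own entry, because Day 11 evening falls at 240 + x, below 252. Extending the 240-hour row down to 222 instead would leave 216 hours empty.
2. **Last row:** replace 528 hours by Day 22 (504 hours) and define it by calendar day, Day 19 to Day 25, as in Table 2-2. Calendar days are safer than 504 ± 72 = 432 to < 576 hours, which would lose Day 19 visits earlier in the day than the dose and Day 25 visits at or after the dosing clock time. State which table governs the Day 22 EQ-5D-5L.

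While the table is open, check the other once-daily labels. The values 216, 240, 336 and 528 equal Day × 24 for Days 9, 10, 14 and 22, whereas the SAP's numbering needs (Day − 1) × 24. A Day 14 evening entry, at 312 + x hours, falls in the 312-hour row for x < 12 and leaves the 336-hour row empty.

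The cost is a table edit with no new data. Some 216-hour values would be up to 12 hours late instead of 6, a tolerance the 240- to 336-hour rows already allow. The window becomes asymmetric at that one time point, which a table footnote should state.
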